## **Design and Outcomes**

This is a pragmatic superiority trial to examine the strengths and weaknesses of COPES asynchronous (IVR-CBT-CP) versus synchronous CBT-CP using three aims. Aim 1: Using a randomized pragmatic trial design in 764 VHA patients, we will determine whether COPES+UC is superior to synchronous CBT-CP+UC at 4 (primary endpoint), 6 and 12 months post-enrollment on: 1) A measure of pain functioning (the interference subscale of the Brief Pain Inventory (BPI)-primary outcome), 2) NRS pain intensity, catastrophizing, insomnia, depression, pain self-efficacy, and treatment satisfaction, treatment dose, and Patient Global Impression of Change (4 months only). Tertiary outcomes include patient engagement (a patient attending at least one session of CBT-CP or completing at least one treatment week of COPES), time to first treatment session, time to complete treatment, number of participants who complete all 10 treatment sessions (completion=yes/no). . and 3) health care use including emergency and urgent care, and pharmacological and non-pharmacological pain care.

Evaluate uptake, engagement, and variation in outcomes across groups where treatment disparities are possible (e.g., gender, race/ethnicity) and among patients with co-morbid alcohol and substance use disorders that have traditionally been excluded from trials of non-pharmacological interventions.

Aim 2: Evaluate the intervention delivery costs of COPES and conduct a budget impact analysis.

Aim 3: Conduct a process evaluation using the Consolidated Framework for Implementation Research (CFIR) and RE-AIM to guide our evaluation. We will:

3a. Conduct CFIR-guided interviews with the coordinating site's clinicians (VACHS) and study site clinicians and administrators to assess their experience with and views regarding the COPES and CBT-CP interventions

3b. Communicate ongoing implementation findings with participating sites and stakeholders.

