### 5.3 Concomitant Interventions

#### 5.3.1 Allowed Interventions

We anticipate that patients will continue to engage in usual pain care. Information about participants' use of inpatient and outpatient care will be obtained from the EHR (see Table 4). We will extract from the EHR instances of pharmacological and non-pharmacological pain care received by COPES and CBT-CP participants beginning at randomization (baseline). Because complementary and integrative health (CIH) interventions and pain-specific psychological interventions are not uniformly coded and can therefore be difficult to identify in the EHR, we will work with study sites during the UG3 planning phase to identify local pain care offerings and coding practices for these interventions. One of the final steps will be collecting information regarding CIH offerings at the site and specific coding practices for these offerings. This information will be obtained through a combination of a survey and informational interview with local site personnel. We will assess experience with the most common CIH interventions during the screening assessment call using the PMC3 harmonized measure. We will ask patients about pain treatment received outside of VHA.

Table 4 Components of Usual Pain Care

EHR Identified	Treatment identified with local input
Physical therapy	CBT-CP
Injections	Yoga
Chiropractic care	Mindfulness meditation and Mindfulness-based Stress Reduction

TENS	Acceptance and commitment therapy (ACT)
Spinal cord stimulator	Pain school or other behavioral + PT or exercise
Pain Clinic	Tai Chi
Physiatry	Massage
Emergency and urgent care	Acupuncture
Opioid pain medication dispensed	
Non-opioid pain medication dispensed	

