*Non-opioid pain medications dispensed.* Dispensed non-opioid pain-related medications also will be extracted, including topical analgesics, non-steroidal anti-

inflammatory drugs, anticonvulsants, and antidepressants (specifically, selective serotonin and norepinephrine reuptake inhibitors and tricyclic antidepressants as in Dorflinger et al.).

*Non-pharmacological pain care.* Visits to specialty services associated with non-pharmacological pain care will be extracted from the EHR using clinic stop codes. These services include physical therapy, physiatry, multidisciplinary pain clinic, chiropractic care, CIH, pain school, and psychological interventions pertaining to pain (CBT-CP, ACT, biofeedback). Non-pharmacological pain care will be assessed in the 12 months leading up to enrollment for the baseline assessment. Subsequent assessments will include all instances of non-pharmacological pain care since the prior assessment.

*Use of emergency department and urgent care, VHA services.* Emergency department and urgent care visits will be extracted from the EHR using stop codes 130 and 131. We do not have access to non-VA emergency and urgent care and will not collect this data.

*Mental Health and other Physical Comorbidities.* Comorbid mental health diagnoses will be identified when two or more of the same outpatient diagnosis codes are assigned within 18 months, or one or more inpatient codes). Mental health conditions will include depressive disorders (i.e., major depressive disorder, dysthymia, depression due to other causes or not otherwise specified), anxiety disorders (i.e., anxiety disorder not otherwise specified [NOS], panic disorder, generalized anxiety disorder, agoraphobia with and without panic, other anxiety states), bipolar disorder, PTSD, alcohol use disorders, and drug use disorders. Other physical health conditions will be identified in the same manner. These include conditions contained on the Charlson Comorbidity Index.

*Daily IVR assessment calls.* COPES participants will undergo daily IVR assessment of pain intensity, pain interference, pedometer-measured step counts, sleep quality, sleep duration, and positive and negative affect for seven days to establish a baseline of function for the purposes of treatment.

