Intensity of Service Use. As exploratory analyses, we will compare service utilization during the 12 months post-baseline by category (e.g., dose of opioid medication dispensed (continuous variable), number of PCP visits (count), non-opioid medication dispensed (binary), non-pharmacological pain care (binary), use of emergency department (binary) and urgent care (binary)) between groups using linear/generalized linear mixed models with an appropriate outcome distribution. We will also consider two-parts models for the opioid dose and PCP visits outcomes in case of zero-inflation. We will conduct a budget impact analysis and will include the cost of the intervention (personnel, supplies, CBT therapist training, and IVR fixed/variable costs) as well as costs for specific medical care services likely to be affected. Data from CBT therapists time records will be combined with wage data from the VA Financial Management System to produce estimates of intervention-specific personnel costs. Costs associated with the use of specific medical care services, such as medications, will be obtained from the VA Managerial Cost Accounting (MCA) System. Cost analysis will be conducted in accordance with the guidance provided by Sullivan et al. including the use of sensitivity analysis and scenarios that allow for varying assumptions about intervention uptake, compliance or component costs. All resource use and cost comparisons will be adjusted for any observed differences in baseline characteristics. Because costs of resource utilization are usually skewed, alternative modeling techniques (e.g., log-transformed costs, negative binomial regression)

will be used. Information on non-VA care will be collected by automated IVR call assessment. To mitigate recall bias, we will use a two-time frame method that asks about utilization over the past 6 months and over the past 2 months with more weight given to the shorter timeframe.

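### The exploratory 12-month comparison of non-pharmacological pain care does not exclude the assigned CBT-CP course, so it mixes study treatment with other care

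*Combined protocol and SAP*

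**What the plan says.** The Précis (Design and Outcomes, Aim 1) compares COPES plus usual care with synchronous CBT-CP plus usual care. Its outcomes include "health care use including emergency and urgent care, and pharmacological and non-pharmacological pain care".

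Section 9.6 (Intensity of Service Use) gives the analysis: "As exploratory analyses, we will compare service utilization during the 12 months post-baseline by category". One category is a yes/no item for non-pharmacological pain care, listed with others as "non-pharmacological pain care (binary), use of emergency department (binary) and urgent care (binary)) between groups".

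Section 6.2.2 (Baseline Assessments) takes that item from clinic stop codes in the electronic health record (EHR). The qualifying services include "chiropractic care, CIH, pain school, and psychological interventions pertaining to pain (CBT-CP, ACT, biofeedback". The counting rule after baseline is "Subsequent assessments will include all instances of non-pharmacological pain care since the prior assessment". Section 5.3.1 sets the start of capture: care "received by COPES and CBT-CP participants beginning at randomization (baseline". Table 4 in that section lists CBT-CP among the components of usual pain care.

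The control arm's assigned treatment is ordinary CBT-CP at the local VA. Sections 5.4 and 10.3.5 say that every synchronous session is entered in the EHR. Section 4.3 says that the study consult follows the same route as a non-study referral. COPES is delivered centrally, and Sections 5.4, 10.1 and 10.3.5 measure participation in it from the IVR system. No section removes the assigned course from the service-use item.

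**The concern.** The Aim 1 framing separates the assigned treatment from usual care, so the natural question is whether the arms differ in the other pain care that patients use. The written definition puts the control treatment back into that measure. Because the item is yes/no, a single assigned session is enough to change it.

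A gap produced this way could be read as COPES reducing use of non-drug pain care, or as synchronous treatment increasing it, when care outside the trial did not differ. It could also hide a real difference in the opposite direction. The Précis says that the trial should inform policy and treatment recommendations, so an exploratory result of this kind may still be quoted.

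The mental-health visit count in Section 9.5.2 is exposed in the same way if CBT-CP sessions carry mental-health codes.

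**Working it through.** **Arm size.** The plan states no figure for this item, so the only number to reproduce is the arm size. With SD 2.4, difference 0.55, two-sided alpha 0.05 and 80% power (Section 9.2), n = 2(1.960 + 0.842)² × 2.4² / 0.55² ≈ 299 per group, against 305 stated. Power at 305 is 80.8%. Allowing for 20% attrition, 305 / 0.8 = 381.25, so 382 per group and 764 in total. This reproduces. I use 382 per arm below and ignore therapist clustering.

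**Assumed inputs (the documents give none of these).**
- p: share using *other* non-pharmacological pain care within 12 months, the same in both arms, so there is no true difference.
- e: share of the synchronous arm attending at least one session.
- c: share of engaged COPES participants whose contacts are coded as CBT-CP encounters.
- p and e are independent, and an attended synchronous session is picked up by the codes.

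**Formulas.** Counted synchronous rate = 1 − (1 − p)(1 − e). Counted COPES rate = 1 − (1 − p)(1 − c·e₂), where e₂ is COPES engagement. False gap = (1 − p)(e − c·e₂).

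**COPES contacts not coded (c = 0).** Synchronous versus COPES, in percent, with the gap in points:

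| p | e = 0.4 | e = 0.6 | e = 0.8 |
|---|---|---|---|
| 0.2 | 52 v 20 (+32) | 68 v 20 (+48) | 84 v 20 (+64) |
| 0.4 | 64 v 40 (+24) | 76 v 40 (+36) | 88 v 40 (+48) |
| 0.6 | 76 v 60 (+16) | 84 v 60 (+24) | 92 v 60 (+32) |
| 0.8 | 88 v 80 (+8) | 92 v 80 (+12) | 96 v 80 (+16) |

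The odds ratio runs from 1.83 (p = 0.8, e = 0.4) to 21 (p = 0.2, e = 0.8). At p = 0.4, e = 0.6 it is (0.76/0.24)/(0.40/0.60) = 4.75. The chance of a significant result with no true difference is 86% in the mildest cell and above 99% in all the others. Engagement of 11%, 17%, 24% and 37% at p = 0.2, 0.4, 0.6 and 0.8 is already enough for about an 80% chance.

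**Masking.** Take p = 0.4 in the synchronous arm, e = 0.6, and true other-care use of 0.5 in COPES. The counted contrast is 0.50 − 0.76 = −0.26. A true 10-point excess in COPES appears as a 26-point deficit.

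**COPES contacts coded.** With c = 0.5 and equal engagement, each gap in the table halves. With c = 1 and equal engagement, the gap is 0. With c = 1 and COPES engagement 15 points higher, it is −0.15(1 − p): −12 points at p = 0.2 and −3 points at p = 0.8.

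**After exclusion.** With no true difference, the expected gap is 0 and the rejection rate is 5%. A true 10-point difference in other care would have about 89%, 80% and 83% power at lower-arm rates of 20%, 40% and 60%.

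**The case against.** The strongest reply is that this is incomplete wording on one exploratory variable. Table 4 sits under concomitant interventions, and the arms are described as treatment plus usual care, so the investigators may well mean other care only. CBT-CP also has a proper place in the list, both for the 12 months before enrollment and for detecting crossover in the COPES arm. That is fair as to intent, but the stated rule counts all instances after randomization, and a programmer following it would include the assigned sessions.

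Three stronger readings are tempting, and the documents do not support them.

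- *Use must be higher in the synchronous arm by construction.* This requires COPES contacts to be uncoded. Sections 5.4 and 10.3.5 point that way by referring to synchronous sessions and taking COPES participation from the IVR system. However, Sections 9.6 (Tertiary Analysis) and 10.1 speak of all sessions being in the EHR, and the Section 5.4 table takes engagement from notes or CPT codes without naming an arm. Section 9.4 expects the monitored indicators, engagement among them, to favor the IVR arm, so with full coding the gap could reverse. Section 5.3.1 also warns that pain-specific psychological care is not uniformly coded, and Table 4 places CBT-CP among treatments identified with local input. A recorded session is therefore not certain to set the flag. Incomplete capture shrinks e in the formula.
- *The health-care-use objective cannot be answered.* Only one category is affected. Opioid dose, non-opioid medication, primary care visits, and emergency and urgent care do not contain the assigned sessions.
- *The budget impact analysis double counts these sessions.* Section 9.6 includes both intervention cost and medical service cost, but does not say which holds the synchronous sessions. Double counting is a possibility, not a demonstrated error.

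The size also depends on chosen inputs. Section 5.4 says that dropout in prior trials was most frequent before any session, so low engagement is plausible. The broad service list makes high p plausible. That corner of the table gives 8 points.

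**Conclusion.** The point holds for one exploratory item. As defined, the yes/no non-pharmacological pain care comparison can count the control arm's assigned treatment, and no section excludes it. If COPES contacts are not coded as CBT-CP encounters, the false excess in the synchronous arm is about 8 to 64 points over p = 0.2–0.8 and e = 0.4–0.8, given independence and capture of the sessions by the codes used. If COPES contacts are coded, the gap may be smaller, absent or reversed, and the flag partly records engagement. On neither branch does the item show whether the arms differ in other non-pharmacological care. Mental-health visits share the problem only where sessions carry those codes. The primary outcome is not touched. The matter deserves correction because the contrast could mislead and the remedy is cheap.

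**What to change.** In Section 9.6 (Intensity of Service Use), define post-randomization non-pharmacological pain care as care other than the assigned course: exclude synchronous CBT-CP delivered under the study consult and any COPES encounter. Apply the same exclusion to the mental-health visits in Section 9.5.2 where sessions carry those codes. State how COPES contacts are coded in the EHR.

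Report the assigned sessions under dose and engagement. Keep non-study CBT-CP in the COPES arm and report it as crossover.

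In the budget impact analysis, do not remove synchronous sessions from costs; state only that their cost is counted once. The time log in Section 9.6 (Resource Use) is entered on the IVR therapist interface, and no log for local clinicians is described. Dropping the sessions from service use could therefore lose the control arm's treatment cost.

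The cost is a definition in the plan and one programming step. Section 4.3 already tracks study consults, and Section 5.4 already collects attendance by chart review. No new data collection is needed.

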
Randomization Participants will be randomized in a 1:1 ratio to one of the two treatments (COPES or CBT-CP). The randomization sequence will be generated by the study statistician using statistical software and concealed in the study database until the time of randomization. Randomization will be stratified by site and gender

and will be done according to a permuted block design with variable block size (4 and 6) to maintain balanced treatment assignment.

A waiver of informed consent for recruitment purposes has been obtained, for recruitment and initial study screening.

A waiver of documentation of informed consent has been obtained for the intervention. The information sheet will be available on the study website, as explained, or participants will be mailed an information sheet if they request it. Certificate of confidentiality language will be included.

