## **9.2 Sample Size and Randomization**

Assuming a standard deviation of BPI interference of 2.4 (as observed in a previous study (SCOPE)), a total sample size of 610 subjects (305 per group) would provide 80% power to detect a mean difference in BPI interference of 0.55 between groups at 4 months using a two-sided t-test at significance level  $\alpha=0.05$ , and 90% power to detect a difference of 0.63. To account for an expected attrition rate of 20%, we will enroll a total of 764 participants (382 per group). Half of the participants will be female.

Although the randomization will be done at the patient level, there may be some clustering due to the therapist delivering the intervention. We conducted a simulation study to investigate the effect of this clustering on power. We assumed that in the COPEs arm (treatment delivered remotely by IVR) 9 therapists will be delivering the intervention (each to an equal number of subjects), and in the synchronous CBT arm 38 therapists will be delivering the intervention. Based on a prior pain trial of group cognitive behavioral treatments, we used an estimate of therapist-level intracluster correlation coefficient (ICC) of 0.01. Simulations (N=100000) showed that we will

have at least 84% power to detect a difference in BPI of 0.65 with an ICC of 0.01 or less using a mixed model on the outcome at 4 months with a therapist random effect.

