## **9.6 Data Analyses**

Quantitative Analysis. As an estimate of uptake, we will present the proportion of patients who agree to be randomized out of all who are offered referral to treatment in our study. Randomization success will be assessed by side-by-side summaries of

baseline demographic and clinical characteristics of subjects by treatment group. Analyses of all outcomes will be done according to the intent-to-treat principle.

Primary Analysis. We will test and estimate the difference between COPES and CBT-CP in terms of BPI interference by using a linear mixed-effects model which simultaneously models all available BPI interference measurements including baseline. The model will contain fixed effects for treatment (categorical: COPES vs. CBT-CP), site (categorical), gender (categorical), time (categorical: baseline, 1, 4, 6, 12 months), and the treatment-by-time interaction. The only covariates that will be included in the primary and secondary analysis (including subgroup analyses) are site and gender. We are adjusting for these 2 variables because they are used for stratification in randomization. An unstructured variance-covariance matrix will be used to model correlations among repeated measures within a subject, and a therapist random effect will be used to model the correlation of outcomes in subjects who share the same therapist. Because this is a randomized trial, in the model above we will impose the constraint that the means for the two groups are equal at baseline (that is, we will perform a constrained longitudinal data analysis). Following the CONSORT recommendations, we will not perform any test for baseline differences as these tests are not needed in a randomized clinical trial “Such significance tests assess the probability that observed baseline differences could have occurred by chance; however, we know that any differences are caused by chance” This model will allow us not only to assess the between-group difference at 4 months (primary endpoint), but also to evaluate in secondary analyses whether between-group differences are maintained over time (at 6 and 12 months). Results will be summarized as least-squares means (and their 95% confidence interval) within and between groups. The primary analysis will be conducted at significance level 0.05.

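### The exploratory service-use comparison reduces four outcomes to any/none over 12 months although visits are extracted, so it cannot show a change in intensity and can lose a substantial share of power

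*Combined protocol and SAP*

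**What the plan says.** The paragraph on intensity of service use in section 9.6 compares the arms over the 12 months after baseline and calls these analyses exploratory. Its examples keep opioid dose continuous and primary care visits as a count, with two-part models considered for those two if zeros are in excess. Non-opioid dispensing is labelled binary, and so are the next three items: "non-pharmacological pain care (binary), use of emergency department (binary) and urgent care (binary". No reason is given for the difference.

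The data are finer than that. Under Baseline Assessments in section 6.2.2:
- For non-pharmacological care: "Subsequent assessments will include all instances of non-pharmacological pain care since the prior assessment".
- For emergency and urgent care: "Emergency department and urgent care visits will be extracted from the EHR using stop codes 130 and 131".
- For non-opioid medication, the text says only that dispensed drugs are extracted.

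Section 5.3.1 adds that instances of both pharmacological and non-pharmacological pain care are taken from the record from randomization onwards. The précis (Design and Outcomes) lists health care use as the third item of Aim 1. No rate, dispersion, target effect or power is given for any service-use outcome.

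**The concern.** A comparison headed as one of intensity should be able to detect a change in intensity. Coded any/none over a full year, a participant with one physical therapy visit is the same as one with twenty.

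Participants have chronic pain of at least moderate severity and are expected to continue usual pain care. Two of the categories are also broad. Non-pharmacological care pools physical therapy, physiatry, pain clinic, chiropractic, complementary and psychological care. Non-opioid medication pools topicals, anti-inflammatories, anticonvulsants and antidepressants. A large fraction of both arms may therefore be a yes, although the documents give no figure.

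At stake is whether these exploratory comparisons can describe a difference in volume of care if there is one. Counts preserve the any/none result, whereas reporting only any/none does not preserve the counts.

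**Working it through.** **The plan's own figure.** The only sample size is for BPI interference: "Assuming a standard deviation of BPI interference of 2.4" and "80% power to detect a mean difference in BPI interference of 0.55 between groups at 4 months using a two-sided t-test".
- n per arm = 2 × (1.960 + 0.842)² × 2.4² / 0.55² = 2 × 7.849 × 5.76 / 0.3025 = 299, or 300 by the t-test, against the stated 305.
- At 305 per arm, power is 80.8% for 0.55 and 90.0% for 0.63.
- 305 / 0.8 = 381.25, rounded up to 382 per arm, or 764 in total.

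These reproduce, but none concerns service use. They supply only the arm size.

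**Inputs for the check.**
- From the documents: 382 per arm, 1:1 allocation (section 4.3), and two-sided 0.05. That level is stated for the primary analysis only ("The primary analysis will be conducted at significance level 0.05") and is borrowed here.
- Assumed, because the plan gives nothing: mean μ events per year in the reference arm, negative binomial dispersion k (variance μ + kμ²; k = 0 is Poisson), and a constant rate ratio ρ.

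**Formulas.**
- Count model: SE(log ρ) = √{[(1/μ + k) + (1/(μρ) + k)] / n}. ρ is solved so that power is 80%.
- Any use: P = 1 − (1 + kμ)^(−1/k), or 1 − e^(−μ) when k = 0, evaluated at μ and at μρ.
- Any/none test: log odds ratio with SE = √{1/[nP₁(1−P₁)] + 1/[nP₂(1−P₂)]}.
- Power = Φ(|effect|/SE − 1.96) in both cases.

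**One case in full, μ = 1 and k = 1.**
- ρ = 0.742, so |log ρ| = 0.299.
- Count model: SE = √[(2 + 2.348)/382] = 0.1067, and 0.299/0.1067 − 1.96 = 0.84, giving 80%.
- Any use: P₁ = 0.500 and P₂ = 0.426. The log odds ratio is also 0.299, but its SE is 0.1455. Then 0.299/0.1455 − 1.96 = 0.09, giving 54%.

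**Range, k from 0 to 3, count model held at 80%.**

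| Mean per year | P(any), reference arm, k = 0 to k = 3 | ρ, k = 0 to k = 3 | Any/none power over the range |
|---|---|---|---|
| 0.2 | 18% to 15% | 0.59 to 0.52 | 70-77% |
| 0.5 | 39% to 26% | 0.73 to 0.62 | 59-71% |
| 1 | 63% to 37% | 0.81 to 0.66 | 48-60% |
| 2 | 86% to 48% | 0.86 to 0.68 | 37-39% |
| 4 | 98% to 57% | 0.90 to 0.69 | 13-29% |
| 8 | 100% to 66% | 0.93 to 0.70 | 4-22% |

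A two-proportion test in place of the log odds ratio changes these by about one point at most.

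**Simulation check** (600 runs per setting, negative binomial regression against a two-proportion test):

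| Mean | k | ρ | Count | Any/none |
|---|---|---|---|---|
| 0.3 | 1 | 0.65 | 78% | 69% |
| 0.5 | 1 | 0.65 | 90% | 78% |
| 1 | 2 | 0.65 | 91% | 66% |
| 5 | 1 | 0.75 | 96% | 34% |
| 10 | 1 | 0.75 | 95% | 23% |

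The pattern agrees. Site, gender and therapist effects are left out throughout.

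**The case against.** Much can be said for the plan.

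- **Status.** The comparison is exploratory and has no power target. Service use is not among the secondary or tertiary outcomes in section 9.5.2, where it appears with the cost aim. The list is introduced as examples, and models are to use a suitable distribution. This limits how much the point matters. It does not undo the explicit binary labels.
- **Size.** If emergency or urgent-care use is infrequent, about 0.2 per year, the loss is only 3 to 10 points. This stands.
- **Different questions.** Any use and volume of use are different estimands. If an intervention changed only whether care is used at all, any/none would lose nothing. This stands, and is why any/none should be kept.
- **Data quality.** Section 5.3.1 warns that complementary and pain-specific psychological care is coded unevenly and can be hard to find in the record. Counts suffer more than any/none from partly missed visits. Pain care outside VHA is asked about by modality as yes/no (section 6.2.2), so counts would describe VA care only. Both stand as limits on the remedy.
- **Dispensing.** Neither number of fills nor days' supply is stated for non-opioid drugs. Section 5.3.1 makes a count of instances plausible, but no more.
- **Contamination.** Section 6.2.2 includes CBT-CP within non-pharmacological care. A raw count could add up to ten trial sessions for a control participant. Any/none has the same fault, since one session makes a yes. Either analysis needs an exclusion rule.

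A reader might also infer that the yes/no results feed the budget impact analysis. The documents do not say so. Service costs come from the VA cost accounting system and are modelled separately with methods for skewed data, so volume can still appear there.

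**Conclusion.** The point holds as an inexpensive improvement to an exploratory analysis. Four outcomes under a heading about intensity are coded so that intensity cannot be seen. For emergency, urgent-care and non-pharmacological care, the visits are extracted.

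The size depends on rates that the plan does not give. Against 80% for a count model, the assumed loss is 3 to 10 points at a mean of 0.2 per year, 9 to 21 at 0.5 and 20 to 32 at 1. More than half of the power goes only from about 2 events per year. That is plausible for non-pharmacological visits or repeat dispensing, but it is an assumption. All of this supposes a constant rate ratio, negative binomial counts and complete 12-month records for 382 per arm.

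It is tempting to read this as losing most of the power for the whole health-care-use objective. The documents do not support that. Opioid dose and primary care visits keep their scale, costs are analysed separately, and no rate is given that would put emergency or urgent care in the range of heavy loss.

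**What to change.** Amend the service-use paragraph of section 9.6 as follows:
- Analyse emergency, urgent-care and non-pharmacological pain visits as counts, with a negative binomial or two-part mixed model as already contemplated for primary care visits.
- Do the same for non-opioid dispensing instances if the extraction yields them. Otherwise keep that outcome as any/none and say why.
- Exclude the trial's own CBT-CP sessions from non-pharmacological care in both arms, for the count and for any/none.
- Report any/none as the first part of the two-part model or beside the count result.
- State that counts cover care recorded in the VA system, and note the uneven coding as a limitation.

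The cost is a few sentences in the SAP, a rule to identify the trial's sessions, and a little more modelling. For the three visit outcomes, no new data collection is needed.
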